4.4. Treatment Assignment

All eligible participants will receive STAR-0215. In Cohort 1, participants will receive a single dose of STAR-0215. In Cohorts 2 and 3, participants will receive 2 doses of STAR-0215. There is no placebo group in this study. Dose regimen and dose level information for each cohort is provided in Table 4.

4.5. Duration of Treatment and Duration of Study

Individual participants will receive 1 dose of STAR-0215 (Cohort 1; Day 1) or 2 doses (Cohort 2; Days 1 and 84, and Cohort 3; Days 1 and 28). The duration of study participation for each participant, including the Screening and Run-In period, is up to [REDACTED], or [REDACTED] days in Cohorts 1, 2, and 3, respectively. The study is composed of 3 periods, as follows:

- Screening/Run-In: at least 56 days
- Treatment Period: Individual participants will receive STAR-0215 on Day 1 (Cohort 1), Day 1 and 84 (Cohort 2), or Day 1 and 28 (Cohort 3).
- Follow-up Period: approximately 6 months after the last dose of STAR-0215 (Day 168 for Cohort 1, Day 251 for Cohort 2, and Day 195 for Cohort 3). At this time, participants who are willing and eligible to consent can begin participation in the long-term open label extension study (STAR-0215-202).
- Follow-up Period: For participants who do not participate in the long-term open label extension study, monitoring will be performed through [REDACTED] months after the last dose of STAR-0215 in all cohorts (Day [REDACTED] in Cohort 1, Day [REDACTED] in Cohort 2, and Day [REDACTED] in Cohort 3) through regular contacts and scheduled study visit.

4.6. End of Study Definition

The end of the study is defined as the date the last participant is examined for the purposes of final data collection for the overall study.

4.7. Stopping Rules

Table 5: Stopping Rules for Study STAR-0215-201

Adverse Event Criteria	Action
At least 2 participants in a dose cohort experience similar SAEs or At least 2 participants in a dose cohort experience similar Grade 2 treatment-related AEs	The SRC will make a recommendation as to continuation, including potentially modifying the starting dose of the subsequent cohort.
Any 1 participant in a dose cohort experiences a Grade 3 or greater treatment-related AE	Dosing for the participant and the remainder of the cohort will be halted until a review of the event by the SRC is completed and the SRC has made a recommendation.
Any occurrence of a treatment-related SAE	May result in suspension of any further dosing in the study by the Medical Monitor until the SRC has evaluated the event and determined the next appropriate course of action.

Abbreviations: AE = adverse event; SRC = Safety Review Committee; SAE = serious adverse event.

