4. INVESTIGATIONAL PLAN

4.1. Overall Study Design

STAR-0215-201 is a Phase 1b/2, multicenter, single and multiple dose study to assess the safety, tolerability, efficacy, PK, PD, and immunogenicity of STAR-0215 in participants with Type I or Type II HAE.

Properly consented participants will undergo screening assessments according to the inclusion and exclusion criteria ([Section 5.1](#) and [Section 5.2](#), respectively) and immediately enter the Run-In period. During the Run-In period, HAE attack information will be collected to determine if a participant meets the eligibility requirement of experiencing at least 2 HAE attacks during this time period and to establish a baseline prior to STAR-0215 administration. If a participant has an HAE attack during the Run-In period before Day 1 (first dose of STAR-0215), all signs and symptoms of the HAE attack must be resolved before dosing. A washout period for on-demand treatment is not required. The Run-In period may be extended after consultation with the Medical Monitor. In Cohorts 2 and 3, if a participant has an HAE attack immediately before the second dose (Day 84 and Day 28, respectively), signs and symptoms of the HAE attack should be improving per participant report prior to STAR-0215 administration; a washout period for on-demand treatment is not required before the second dose is administered.

In Cohort 1, each participant who has completed the Run-In period and is eligible for STAR-0215 administration will receive 1 dose of STAR-0215 on Day 1. When Cohort 1 has completed dosing, the SRC will review the cohort's cumulative safety data from the Screening/Run-In period through 21 days after dosing. Progression to Cohort 2 dosing will occur if there are no concerning safety signals. Details of the SRC's review are provided in [Section 4.2](#).

In Cohort 2, each eligible participant will receive 2 doses of STAR-0215, the first on Day 1 and the second on Day 84. When 6 participants in Cohort 2 have received Dose 1, progression to dosing of Cohort 3 will begin.

In Cohort 3, each eligible participant will receive 2 doses of STAR-0215, the first on Day 1 and the second on Day 28.

Provided no safety concerns are noted from a cumulative review of safety data from this study and the ongoing FIH study (STAR0215-101), [REDACTED] and [REDACTED] may be explored in [REDACTED] would be added through an amendment to the protocol.

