STAR-0215 will be administered SC into the abdomen. There will be 4 participants in Cohort 1, 6 participants in Cohort 2, and 6 participants in Cohort 3. Based on the accumulated safety information and enrollment as continually monitored by the SRC [REDACTED] up to 6 additional participants may be added to Cohort 2 and/or Cohort 3 (maximum of 12 participants each in Cohorts 2 and 3) after the first 6 participants in Cohort 3 have been enrolled. The dose regimens and dose levels for each cohort are in [Table 4](#). There is no placebo group in this study. An overview of the study design is provided in [Figure 2](#).

As detailed in the Schedules of Assessments (SOAs; [Section 1.1](#)), study assessments will be performed in all cohorts through 6 months after the last dose of STAR-0215 (Day 168 in Cohort 1, Day 251 in Cohort 2, and Day 195 in Cohort 3). At this time, participants who are willing and

[figure not shown]
eligible to consent can begin participation in the long-term open label extension study (STAR-0215-202). For participants who do not enroll in the long-term open label extension study, safety monitoring will be performed through [REDACTED] months after the last dose of STAR-0215 in all cohorts (Day [REDACTED] in Cohort 1, Day [REDACTED] in Cohort 2, and Day [REDACTED] in Cohort 3) through regular contacts and scheduled site visit. Visits subsequent to STAR-0215 administration are scheduled with respect to the actual day of STAR-0215 dosing for consistency and precision in post-dose sample collection. Safety assessments (including AEs, vital signs, ECGs, physical examinations, clinical laboratory evaluations, and pregnancy testing), and efficacy, PK, PD, immunogenicity, biomarker, and [REDACTED] may be conducted at scheduled site visits.

Table 4: STAR-0215 Dose Regimens

Cohort	Dose 1		Dose 2		# Participants
	STAR-0215 Dose Level (mg)	Dosing Day	STAR-0215 Dose Level (mg)	Dosing Day	
1	450	1	NA	NA	4
2	600	1	300	84	6; up to 12
3	600	1	600	28	6; up to 12

Abbreviations: NA = not applicable.

Figure 2: Overview of Study Design

*Participants may opt to participate in the long-term open label extension trial STAR-0215-202

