4.2. Safety Review Committee

The SRC will be composed of a clinician with expertise in HAE, a medical monitor, and representatives from the Sponsor. The SRC will be responsible for making recommendations related to study progression.

The SRC will meet when Cohort 1 has completed dosing and all study visits through 21 days after dosing. The SRC will review the cohort's cumulative safety data, including AEs, results of vital sign assessments, clinical laboratory assessments, and ECG assessments. Cohort 2 will not be dosed until the appropriate data from Cohort 1 have been reviewed by the SRC. There will be ongoing oversight by the SRC, as there may be ad hoc meetings of the SRC upon the emergence of an unexpected safety signal at any time during the study. In the event of emergent safety concerns posing substantial risk to participants, the SRC will consult with the Protocol Stopping Rules (Section 4.7).

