8.4. Assessment of Severity

The severity of AEs will be graded with a scale appropriate for use with people with HAE, who are otherwise generally healthy individuals.

Tables are provided in [Appendix 2](#) to guide investigator assessment of AE severity.

Any AEs that cannot be graded using the scales provided in [Appendix 2](#) will be graded according to the Investigator's medical judgment using the definitions for the severity categories in [Table 8](#).

Table 8: Guide for Grading Adverse Event Severity

Severity	Definition	Grade
Mild	Asymptomatic or mild symptoms; clinical or diagnostic observations only; intervention not indicated	1
Moderate	Minimal, local or noninvasive intervention indicated; limiting age appropriate instrumental Activities of Daily Living	2
Severe	Severe or medically significant but not immediately life-threatening; hospitalization or prolongation of hospitalization indicated; disabling; limited self care Activities of Daily Living	3
Life-threatening	Life-threatening consequences; urgent intervention indicated.	4
Fatal	Death related to an adverse event	5

It is important to distinguish between serious and severe AEs. Severity is a measure of intensity whereas seriousness is defined by the criteria in [Section 8.2.2](#). An AE of severe intensity may or may not be considered serious.

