Bradycardia - beats per minute***	50 – 54	45 – 49	< 45	ER visit or hospitalization for arrhythmia

Vital Signs *	Mild (Grade 1)	Moderate (Grade 2)	Severe (Grade 3)	Potentially Life-Threatening (Grade 4)
Hypertension (systolic) - mm Hg	141 – 150	151 – 155	> 155	ER visit or hospitalization for malignant hypertension
Hypertension (diastolic) - mm Hg	91 – 95	96 – 100	> 100	ER visit or hospitalization for malignant hypertension
Hypotension (systolic) – mm Hg	85 – 89	80 – 84	< 80	ER visit or hospitalization for hypotensive shock
Respiratory Rate – breaths per minute	17 – 20	21 – 25	> 25	Intubation

Source: [FDA 2007](#)

* Subject should be at rest for all vital sign measurements.

** Oral temperature; no recent hot or cold beverages or smoking.

*** When resting heart rate is between 60 – 100 beats per minute. Use clinical judgement when characterizing bradycardia among some healthy subject populations, for example, conditioned athletes.

Systemic (General)	Mild (Grade 1)	Moderate (Grade 2)	Severe (Grade 3)	Potentially Life-Threatening (Grade 4)
Nausea/vomiting	No interference with activity or 1 – 2 episodes/ 24 hours	Some interference with activity or > 2 episodes/24 hours	Prevents daily activity, requires outpatient IV hydration	ER visit or hospitalization for hypotensive shock
Diarrhea	2 – 3 loose stools or < 400 gms/ 24 hours	4 – 5 stools or 400 – 800 gms/ 24 hours	6 or more watery stools or > 800 gms/ 24 hours or requires outpatient IV hydration	ER visit or hospitalization
Headache	No interference with activity	Repeated use of non-narcotic pain reliever > 24 hours or some interference with activity	Significant; any use of narcotic pain reliever or prevents daily activity	ER visit or hospitalization
Fatigue	No interference with activity	Some interference with activity	Significant; prevents daily activity	ER visit or hospitalization
Myalgia	No interference with activity	Some interference with activity	Significant; prevents daily activity	ER visit or hospitalization
Illness or clinical adverse event (as defined according to applicable regulations)	No interference with activity	Some interference with activity not requiring medical intervention	Prevents daily activity and requires medical intervention	ER visit or hospitalization

Source: [FDA 2007](#)

B. Tables for Laboratory Abnormalities

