## 2.5 [REDACTED]

In preparation for future clinical development of STAR-0215 and subsequent study planning, [REDACTED] of data in accumulating cohorts are planned (Table 5). The [REDACTED] [REDACTED] was planned to occur after the [REDACTED] in [REDACTED] reaches the [REDACTED] visit. However, enrollment into the study was faster than anticipated and the [REDACTED] [REDACTED] in [REDACTED] have the [REDACTED] visit [REDACTED] [REDACTED] participants have data up to 90 days post first dose therefore it was decided that the [REDACTED] will include the [REDACTED] visit for these [REDACTED] and all other available data from [REDACTED]. In addition, for the same reasons, the [REDACTED] will occur after the [REDACTED] in [REDACTED] reaches [REDACTED] of STAR-0215 (the [REDACTED] visit) and will include all available data from [REDACTED]. At each [REDACTED] the Sponsor will review the accumulated safety, efficacy, PK, PD, and immunogenicity data. If no safety concerns are noted following [REDACTED], efficacy, PK, PD, and immunogenicity results may inform the decision to add additional participants to Cohorts 2 or 3 (up to a total of 12 in each) and/or [REDACTED] exploring [REDACTED] and [REDACTED].

A [REDACTED] will occur when the first 16 participants dosed complete the study. Separate analyses of the 'Initial 16 Participants' and cumulative data for all participants dosed at the time of data cut-off will be performed on the accumulated safety, efficacy, PK, PD, and immunogenicity data.

The IA will summarize safety, efficacy, PK, PD and immunogenicity (ADA) by cohort; as described in section 6 and per Table 5. Listings and figures will also be provided.

Additional ad hoc or unplanned administrative analyses may be performed to monitor safety, PK, PD, ADA and/or efficacy.

**Table 5:** [REDACTED]

[REDACTED]	[REDACTED]	[REDACTED]	[REDACTED]
[REDACTED]	[REDACTED] in [REDACTED] reaches the [REDACTED] [REDACTED] visit	All available cumulative safety, PK, PD, immunogenicity, and efficacy data through the [REDACTED] visit in [REDACTED] and the [REDACTED] visit in [REDACTED]	
 
• Potential addition of up to 6 participants to Cohort 2 (maximum of 12 participants total)
 
• [REDACTED]
 
• [REDACTED]
 

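### The one mandatory dosing halt stops only the affected cohort, although Cohorts 2 and 3 can dose in parallel and both start at 600 mg

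*Protocol*

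**What the plan says.** Table 5 in Protocol Section 4.7, reproduced as Table 4 in SAP Section 2.3, sets three tiers.

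- **Row 1** (similar SAEs, or similar Grade 2 related AEs, in at least two participants of a cohort): the SRC makes a recommendation. No halt is attached.
- **Row 2** (a single participant with a related AE of Grade 3 or above): "Dosing for the participant and the remainder of the cohort will be halted until a review of the event by the SRC is completed". Dosing resumes only once a recommendation has followed that review.
- **Row 3** (any treatment-related SAE): "May result in suspension of any further dosing in the study by the Medical Monitor until the SRC has evaluated the event".

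On timing, Protocol Section 4.1 states: "When 6 participants in Cohort 2 have received Dose 1, progression to dosing of Cohort 3 will begin". Table 4 of the protocol gives Cohort 2 600 mg on Day 1 and 300 mg on Day 84, and Cohort 3 600 mg on Days 1 and 28. Section 4.1 also allows that "up to 6 additional participants may be added to Cohort 2 and/or Cohort 3". On oversight, Section 4.2 says that "there may be ad hoc meetings of the SRC upon the emergence of an unexpected safety signal at any time during the study". On severity, Section 8.4 notes: "An AE of severe intensity may or may not be considered serious".

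**The concern.** A halt confined to one cohort works when cohorts run in sequence behind a review. That describes Cohorts 1 and 2: under Section 4.2, Cohort 2 is not dosed until the SRC has seen the Cohort 1 data through 21 days. For Cohort 3 the stated trigger is only a count of first doses in Cohort 2. The two cohorts can therefore be dosing at the same time, from the same 600 mg starting dose, while the mandatory halt recognises only one of them.

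Safety and tolerability is the primary objective. What is at stake is whether participants due the same dose that preceded a Grade 3 or greater related AE are held automatically until the SRC has looked at it, or only if someone decides to hold them.

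**Working it through.** The plan states no figure on this point, so there is nothing to reproduce. The check has four steps.

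**1. Scope and force of each row.** Row 1 carries a recommendation only. Row 2 is mandatory and limited to the cohort. Row 3 can reach the whole study, but it is discretionary and applies only to related SAEs. No row requires a hold in another cohort.

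**2. Events that trigger row 2 but need not trigger row 3.** Section 8.4 separates severity from seriousness. In the systemic table of Appendix 2, an illness is Grade 3 if it "Prevents daily activity and requires medical intervention"; an emergency room visit or hospitalization appears only at Grade 4. Injection-site erythema above 10 cm is also Grade 3. Such events can be non-serious.

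**3. Can the cohorts overlap?** Inputs are the dosing days in Protocol Table 4 and the windows in Protocol Tables 2 and 3. Let calendar day 0 be Dose 1 of the sixth Cohort 2 participant, so that study Day d falls on calendar day d − 1.

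- That participant's Dose 2: 84 − 1 = 83, or with ±3 days, calendar days 80 to 86.
- A Cohort 3 participant starting on day 0 has Dose 2 at 28 − 1 = 27, or with ±2 days, days 25 to 29.
- 83 − 27 = 56. A Cohort 3 participant who starts by day 56 is nominally due both 600 mg doses no later than that Cohort 2 participant's second dose.

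The schedule therefore permits overlap. How much occurred is not stated. SAP Section 2.5 says that "enrollment into the study was faster than anticipated", which is consistent with overlap but does not measure it.

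**4. Which doses are affected?** At base size, when Cohort 3 opens, the doses still to give are at most 6 × 1 = 6 in Cohort 2 (300 mg) and 6 × 2 = 12 in Cohort 3 (600 mg).

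| Row 2 event | Mandatory halt now | Added by a same-or-higher-dose rule |
|---|---|---|
| Cohort 2, after 600 mg | remaining Cohort 2 doses (at most 6 at base size, all 300 mg) | outstanding Cohort 3 doses, since 600 ≥ 600 (at most 12) |
| Cohort 2, after 300 mg | remaining Cohort 2 doses | outstanding Cohort 3 doses, since 600 ≥ 300 |
| Cohort 3, after 600 mg | remaining Cohort 3 doses | none of the initial Cohort 2 second doses, since 300 < 600; up to 6 expansion first doses, since 600 ≥ 600 |

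The 12 is a ceiling, because only doses falling due before the SRC review are exposed. The earliest Cohort 3 second dose is Day 28 − 2 = Day 26, which is 26 − 1 = 25 days after Day 1. A review shorter than 25 days can therefore catch at most one dose per Cohort 3 participant, or six at base size. The documents give no time limit for the SRC review and no reporting deadline for a non-serious Grade 3 AE (the 24-hour rule in Section 8.6 covers SAEs), so the count cannot be narrowed further.

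**The case against.** The strongest reply is that the tiers are a deliberate choice. Every row 2 event goes to the SRC, whose recommendation has no stated cohort limit, and a medical monitor sits on that committee. Before it meets, other routes exist:

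- Section 4.2 allows ad hoc SRC meetings.
- Section 8.6 promises investigators prompt notice of findings suggesting significant risk, and Section 5.3 lists investigator discretion as a reason to discontinue study drug.
- Section 8.2.2 counts important medical events as serious, so some Grade 3 events would also reach row 3.
- Section 12.9 lets the Sponsor stop the study at any time.

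Appendix 2 is also a vaccine scale for healthy volunteers with low Grade 3 thresholds, so an automatic halt beyond the cohort could be out of proportion. Phase 1a includes single subcutaneous doses up to 1200 mg, twice the 600 mg used here.

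Much of this stands. It narrows the gap to the interval before the SRC review and lowers the urgency. It does not close the gap, because for the other cohort each of these routes depends on someone choosing to act. The Phase 1a data come from single doses in healthy adults. The proportionality argument favours a rule limited by dose and by time, and that can be written.

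A reader might infer more than the documents support: that the other cohort would keep dosing without oversight, that all twelve 600 mg doses would be given before anyone intervened, or that the weakness is equal in both directions. The safeguards above answer the first, the review interval the second, and the 300 mg second dose in Cohort 2 the third. Nor do the documents show that such an event occurred during overlapping dosing.

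**Conclusion.** The point holds as a limited gap in the stopping rule, and it is worth correcting. Row 2 is the only mandatory halt and it does not reach a parallel cohort. After a non-serious Grade 3 or greater related AE, or a related SAE for which the Medical Monitor does not suspend dosing, a pause in the other cohort before SRC review is discretionary.

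The substantive case runs from Cohort 2 to Cohort 3. An event after 600 mg holds the remaining Cohort 2 doses, which are 300 mg for the initial six, but not the 600 mg doses falling due in Cohort 3. The exposure is at most 12 doses at base size and probably fewer; the actual number depends on review time and enrolment, which the documents do not fix. From Cohort 3 to Cohort 2 it concerns only expansion participants awaiting a first dose. No event rate is assumed. The conclusion rests on the wording of Table 5 and on Cohort 3 having doses outstanding when the event occurs.

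**What to change.** Add one sentence to row 2 in Protocol Table 5 and SAP Table 4:

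*Pending SRC review, the halt also applies to any participant in another cohort whose next scheduled dose is equal to or higher than the most recent dose received by the affected participant before onset of the event.*

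This names whose dose is compared, ends with the SRC review, and leaves the initial Cohort 2 participants' 300 mg doses unaffected by a Cohort 3 event after 600 mg. Rows 1 and 3 need no change. Counting row 1 events across cohorts, or adding an SRC review before Cohort 3 opens, are options the sponsor may weigh; this point does not depend on them.

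The cost is an occasional short pause. It may move a Day 28 dose outside its ±2 day window, which would affect AUC0-28 (SAP Section 6.5.1) and the comparison of PK profiles between doses (Protocol Section 2.3). For a participant awaiting Dose 1 it may lengthen the Run-In. Section 4.1 permits this after consultation with the Medical Monitor, but it means more time without long-term prophylaxis, which Section 6.3.1 prohibits; on-demand treatment remains available. No extra participants or procedures are needed.

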5. SELECTION AND WITHDRAWAL OF PARTICIPANTS

5.1. Inclusion Criteria

A participant must meet all the following criteria to be eligible for this study.

1. At least 18 years of age at the time of Screening.
2. Willing and able to read, understand, and sign the IRB/IEC/REC approved informed consent form (ICF).
3. Documented diagnosis of HAE (Type I or II). All of the following must be met:
 - a. Documented clinical history consistent with HAE (e.g. SC or mucosal, nonpruritic swelling episodes without accompanying urticaria).
 - b. C1-INH antigen or functional level less than 40% of the normal level. Participants with antigen or functional C1-INH level 40% to 50% of the normal level may be eligible if they also have a C4 level below the normal range and a family history consistent with HAE Type I or II. Testing for C1-INH and C4 will be performed at Screening. Historical test results for C1-INH may be used to confirm eligibility if the screening C1-INH antigen test or functional level or C4 level laboratory values are inconclusive, after discussion with the medical monitor.
 - c. Age at reported onset of first angioedema symptoms 30 years of age or younger, or a family history consistent with HAE Type I or II.
4. Agree not to receive a dose of any vaccine within 7 days before or after STAR-0215 administration.
5. Participants of childbearing potential must have a negative serum pregnancy test at Screening, must not be pregnant or breastfeeding at Screening, and agree to use one of the protocol defined forms of highly effective contraception ([Appendix 1](#)) during the study and for a total of ■ months after the last dose of STAR-0215.

Note: Participants who are not capable of becoming pregnant (e.g. defined as surgically sterile or post-menopausal), per the protocol ([Appendix 1](#)), are not required to use any form of contraception during the study.

6. Participants capable of producing sperm who have partners of childbearing potential must agree to use one of the protocol defined forms of contraception ([Appendix 1](#)) during the study, unless the participant is azoospermic or their partner is surgically sterile as described in [Appendix 1](#).
7. Agree not to donate or store sperm or engage in any other activity intended to produce sperm for the purpose of insemination during the study, unless such sperm were collected before the administration of the first dose.
8. Agree not to donate or store eggs or undergo assisted reproductive or fertility treatment during the study and for a total of ■ months after the last dose of STAR-0215.

9. Experienced at least 2 HAE attacks during the Run-In period, as confirmed by an investigator based on meeting the protocol-specified definition of an HAE attack ([Section 7.12](#)).

